17.1 Declaration of Helsinki

The sponsor will ensure that this study is conducted in accordance with the ethical principles that have their origins in the Declaration of Helsinki.

17.2 Good Clinical Practise

The trial will be carried out in accordance with the principles of the International Conference on Harmonisation Good Clinical Practice (ICH-GCP) guidelines.

17.3 Approvals

Required documents including the protocol, informed consent form, participant information leaflet, and any other required documents will be submitted to a recognised research ethics committee (REC) (Galway University Hospitals Research Ethics Committee) and the HPRA for written approval, as per submission requirements.

The sponsor will submit and obtain approval from the above parties for substantial amendments to the original approved documents.

17.4 Scopolamine benefits and risks assessment

Bipolar disorder is one of the top 20 leading causes of disability worldwide, with a similar disability adjusted life year rate (138.3 per 100,000) to more prevalent conditions such as asthma (147.9 per 100,000) and Alzheimer's disease (108.5 per 100,000) (Ferrari et al., 2016). Current pharmacological treatments for bipolar disorder and in particular for the

management of depressive episodes in bipolar disorder remain sub-optimal, with pharmacological strategies employed to date often only partially effective (Fournier et al., 2010; Yildiz et al., 2011). In addition to the time duration for treatment response, multiple treatment trials are also often required, thus increasing patient discomfort and distress (Insel and Wang, 2009). Consequently, pharmacological mechanisms that potentially alleviate depressive symptomatology in bipolar disorder and ameliorate patient functioning could present an additional pharmacological strategy for the management of bipolar disorder. A number of recent studies have suggested that scopolamine, the agent being investigated in this study (a pan muscarinic (M) receptor antagonist) can elicit a rapid anti-depressant response in both major depressive disorder and bipolar disorder (Ellis et al., 2014; Furey et al., 2006; Drevets et al., 2010) and thus may present a novel therapeutic strategy, particularly for the management of BPD, in individuals experiencing depressive episodes (Janowsky, 2011).

It is envisaged that the potential burden of the study will be less than the potential value of this research, but there are no guaranteed direct benefits. Participants may benefit indirectly from participation in terms of increased awareness of mental health issues. Some participants may benefit from scopolamine administration in attaining a rapid treatment for their depressive episode.

This study will not include incapacitated adults or children (<18 years of age). Issues regarding specific vulnerable populations are addressed individually below.

- (i) The study requires inclusion of adults with mental illness to address the research question. Only those who have the capacity to provide valid informed consent will be invited to participate. Where there is concern expressed about the capacity of a person to make a decision regarding treatment, a capacity assessment will be performed by the principal investigator or sub-investigator to ensure that participants are able to provide written informed consent.
- (ii) Women of childbearing age are defined by the Irish Central Statistics Office as women of ages 15-49 years (Census 2011, This is Ireland (Part 1) – Central Statistics Office). Women of this age group will not be excluded from this study as this group constitutes a significant proportion of the population of interest (1% of all women) experience bipolar disorder with this disorder usually have its onset in individuals aged 20-45 years of age. Bipolar disorder is equally common in men and women (Kroon et al., 2013) and thus the primary study objective cannot be accurately achieved without including women of childbearing age. At screening visit, precautions will be taken, as detailed in section 8.4.7, in relation to advice on adequate contraception use between Visit 1 to Visit 5.

17.4.1 Physical Risks

17.4.1.1 Tolerability and Adverse Effects of IV Scopolamine

Pulsed IV infusion (4 µg/kg over 15 minutes) has to date been well tolerated with no significant adverse effects (AEs) encountered in other studies that have administered this agent on a similar time regime and at a similar dose to the proposed study (Fury and Drevets, 2010, Fury et al., 2012)

17.4.1.2 Risks secondary to Phlebotomy

Phlebotomy is rarely associated with serious adverse effects and will be performed in this study by experienced delegated staff member of the HRB Clinical Research Facility with phlebotomy experience. Serious side effects such as loss of consciousness and seizures and injury to adjacent structures are rare and vasovagal attacks may occur occasionally. Bruising and small haematoma may occur in approximately 12% of individuals (WHO, 2010). All efforts will be made to reduce the likelihood of adverse events due to phlebotomy, however discomfort during the procedure is common.

17.4.1.3 Risks and hazards secondary to peripheral venous cannulation and intravenous administration of investigative medicinal product (e.g. Scopolamine and 100mls of normal saline or 100mls of normal saline)

Complications that can potentially arise following the procedure of cannulation include infiltration, extravasation, venous spasm, phlebitis, thrombophlebitis, large haematoma, nerve injury, arterial puncture, embolism and needle stick injury (HSE, 2013). In this study, peripheral venous cannulation will be performed using aseptic technique and in accordance with local venous cannulation policy. Cannulation will be utilized for a 15 minute infusion, via a calibrated infusion pump, and be removed prior to discharge from the clinical research facility. The cannulation site will be monitored during the infusion and after cannula removal. Discomfort is common during the insertion of a peripheral venous cannula, however every effort will be made to minimize pain or discomfort, including the use of topical anaesthetics, where indicated.

17.4.1.4 Risks and hazards secondary to IV Scopolamine infusion

AEs that have occurred have been transient in nature (<3 hours) and have included light headedness, sedation, a transiently reduced heart rate and blood pressure (requiring no intervention) and the recognised anticholinergic adverse effects of dry mouth and blurred vision (Drevets and Furey, 2010; Furey and Zarate, 2013).

Pulsed IV administration has not been associated to date with potential AEs noted with high oral dosages including delirium, (hypo)mania, psychosis or disorientation (Furey and Zarate, 2013).

17.4.1.5 Psychological risks

Distress

Some participants may find questionnaires distressing or anxiety-provoking. This is difficult to predict, however researchers will be vigilant for possible negative psychological effects and seek to minimise these wherever possible. Most participants will have experience in answering questions similar to those on the questionnaires and many will previously have completed similar questionnaires. Researchers are all experienced in conducting clinical trials and in research with individuals with bipolar disorder and other major mental illnesses. If participants are distressed, they will be supported and given time out from completion of the questionnaires. If the distress continues, they will be advised that any remaining questionnaires are not required. Where significant distress is present, the clinical team of the participant will be informed by the research team, so that additional support after the clinical visit can be provided.

17.4.1.6 Psychosocial risks

Inconvenience

Attending for assessments or interventions may cause inconvenience to participants. It is anticipated that participants will predominantly reside in Galway or close to Galway. Participant visits will be organised so they will not have to wait prior to review by the researcher.

17.5 Participant confidentiality

The trial staff will ensure that the participants' anonymity is maintained. The participants will be pseudo-anonymised and identified by initials and a participant's identification number on the CRF and any database. All documents will be stored securely. The study will comply with the Data Protection Act and the General Data Protection Regulation (GDPR).

17.6 Other Ethical considerations

The vulnerability of this study group is fully appreciated, and every effort will be undertaken to protect their safety and well-being. During their time on the trial, participants will continue usual care, as recommended by their responsible clinical team. In line with the applicable regulatory requirements, consenting processes will be standardised and a robust SOP for consenting participants will be adhered to.

18. Financing and insurance/indemnity

Indemnity is provided by indemnity cover for research in place from NUI Galway/State Claims agency (Clinical Indemnity scheme) once the trial is approved by a Clinical Research Ethics Committee and regulatory authority.

Funding has been attained from the Stanley Medical Research Institute (SMRI) -Treatment Trials. The SMRI is a non-profit organisation supporting research in the cause of, and treatments for, schizophrenia and bipolar disorder based in the United States of America.

19. Clinical study report and publication policy

The publication policy involves formal presentation of study findings at national and international neuroscience and psychiatry meetings including potentially the College of Psychiatrists of Ireland Winter Conference, Biological Psychiatry annual conference and the International Society for Bipolar Disorder annual conference, following consultation with the sponsor and the HRB-CRFG.

Final findings will be submitted for peer-review and publication in relevant high-impact scientific journals and upon publication may be further publicised in national and international print and electronic media through public relations departments and the NUI Galway website.

Further knowledge dissemination will include registering the trial in the EudraCT database and publication of the trial protocol in a peer-reviewed journal.

Research progress and developments will be presented at in-house research meetings with the Department of Psychiatry at Galway University Hospitals and at the HRB-CRFG.

20. References

- American Psychiatric Association. Diagnostic and Statistical Manual of Mental Disorders (5th Edn) (DSM-V). Arlington, VA APA, 2013.

## 1 Revision History

Revision	Description
1	First Release

## 2 Abbreviations and Definitions

Abbreviation	Full Form
AUDIT	Alcohol Use Disorder Identification Test
CANTAB	Cambridge Neuropsychological Test Automated Battery
CGI-S	Clinical Global Impression-Severity
CRF	Case Report Form
CSR	Clinical Study Report
GAF	Global Assessment of Functioning
HDRS	Hamilton Depression Rating Scale score
ICH	International Conference on Harmonisation
IV	Intravenous
MADRS	Montgomery and Asberg Depression Scale
MedDRA	Medical Dictionary for Regulatory Activities
NEO PI-FFI	NEO Personality Inventory-Five Factor Inventory
POMS	Profile of Mood States
PRISE	Patient Rated Inventory of Side Effects
SAP	Statistical Analysis Plan
SCID	Structured Clinical Interview for DSM
SCOPE-BD	Scopolamine Compared to Placebo in Individuals with Bipolar Disorder who are Experiencing a Depressive Episode
SOC	System Organ Class
VAS	Visual Analogue Scale
YMRS	Young Mania Rating Scale

### **3 Preface**

Bipolar disorder is a chronic disabling psychiatric disorder characterized by recurrent episodes of mania or hypomania and depression. Current pharmacological treatments for bipolar disorder and in particular for the management of depressive episodes in bipolar disorder remain sub-optimal, with pharmacological strategies employed to date often only partially effective.

Putative effect of scopolamine is suggested from animal studies and clinical trials in humans, with a suggestion that the effect was most evident with intravenous (IV) administration of scopolamine. However, studies of IV scopolamine as a treatment agent for depressive episodes to date have had limited numbers of participants and have included heterogeneous populations. This study will be the first to exclusively examine depressive episodes in bipolar disorder to ascertain if a rapid antidepressant effect is demonstrated.

This is the rationale behind the Safety of Scopolamine Compared to Placebo in Individuals with Bipolar Disorder who are Experiencing a Depressive Episode (SCOPE-BD) Trial.

### **4 Purpose of SAP**

This Statistical Analysis Plan (SAP) describes the planned analysis and reporting for the SCOPE-BD Trial. This is a Phase IIb, randomised, double-blinded, placebo-controlled trial of IV Scopolamine in the treatment of reducing severity of depression in individuals with bipolar disorder who are experiencing a depressive episode of at least moderate severity.

The structure and content of this SAP provides sufficient detail to meet all the requirements in accordance with the International Conference on Harmonisation guidance of Statistical Principles in Clinical Trials (ICH E9). All work planned and reported for this SAP will follow internationally accepted guidelines. The following documents were reviewed in the preparation of this SAP:

- Clinical Research Protocol 2017-003112-39 Version 3, 18-Dec-2020.
- Case Report Forms (CRFs).
- ICH E9 and E3

The reader of this SAP is encouraged to also read the clinical protocols for details on the conduct of this study, and the operational aspects of clinical assessments and timing for completing a patient in this study.

## 5 ***Study Objectives and Endpoints***

### 5.1 Study objectives

To assess the efficacy and safety of IV Scopolamine compared to Placebo in Individuals with Bipolar Disorder who are experiencing a depressive episode.

#### ***5.1.1 Primary Objective***

The primary objective is to investigate the efficacy and safety of IV Scopolamine, compared to placebo, in reducing severity of depression in individuals with bipolar disorder who are experiencing a depressive episode of at least moderate severity.

#### ***5.1.2 Secondary objectives***

- To investigate if IV Scopolamine compared to placebo improves mood, cognition and functioning as measured on a number of objective and subjective psychometric instruments in individuals with bipolar disorder experiencing a depressive episode of at least moderate severity.
- To investigate the safety and tolerability of repeated (x3) IV Scopolamine versus placebo in individuals with bipolar disorder experiencing a depressive episode of at least moderate severity.

### 5.2 Study endpoints

#### ***5.2.1 Primary endpoint***

The primary endpoint will be the change in severity of objective depressive symptoms as measured by change in Hamilton Depression Rating Scale score (HDRS) score from pre-randomisation (pre-IV infusion at Visit 3) compared to Visit 6.

#### ***5.2.2 Secondary endpoints***

1. Remission of depressive episode after the last IV treatment (measured objectively at Visit 6), and is defined as occurring when an individual has:
  - (i) a HDRS score <= 7
  - (ii) a Montgomery and Asberg Depression Scale (MADRS) score <6
2. Remission of depressive episode at follow-up (measured objectively at Visit 7)
  - (i) a HDRS score <=7
  - (ii) a MADRS score <6

SCOPE-BD NUIG-2017-002, Statistical Analysis Plan Version 1, 19/03/2024

3. Response to a depressive episode after the last IV treatment (measured at Visit 6) is defined as:

(i) a 50% reduction in MADRS score at Visit 6 compared to Visit 3

4. Response to a depressive episode at follow-up (measured objectively at Visit 7)

(i) a 50% reduction in MADRS score at Visit 6 compared to Visit 3

5. Improvement in mood symptoms measured with the HDRS and MADRS at visits 5, 6 and 7 compared to Visit 3.

6. Improvement in objectively measured overall functioning, measured with the Global Assessment of Functioning (GAF) at Visit 5, 6 and at follow-up at Visit 7 compared to Visit 3

7. Improvement in objectively rated illness severity, measured with the CGI-S at visits 4, 5, 6 and 7 compared to Visit 3 and CGI-I at visits 4, 5, 6 and 7 compared to Visit 3.

8. Changing subjective measured depressive symptoms with the Profile of Mood States (POMS) and Visual Analogue Scale (VAS).

(i) a reduction in POMS score post-infusion compared to pre-infusion at visits 2, 3, 4 and 5 across the six different factors of the POMS (tension, depression, anger, fatigue, vigour and confusion).

(ii) a reduction in VAS scores post-infusion compared to pre-infusion at visits 2, 3, 4 and 5 across 8 items (happy, restless, sad, anxious, anger, drowsiness and alertness).

9. A change in subjectively measured depressive symptoms at Visit 6 compared to Visit 3 as measured with the POMS and VAS.

10. A reduction in subjectively measured depressive symptoms at follow-up (Visit 7) compared to Visit 3 as measured with the POMS and VAS.

11. Psychiatric inpatient admission of a participant due to depressive episodes between Visit 2 and Visit 7.

12. Antidepressants medication use or change by a participant due to depressive episodes over the duration of the study (Visit 2 to Visit 7):

(i) Introduction of a new antidepressant (yes / no)

(ii) Increase in dose of an existing antidepressant (yes / no)

13. Change in motor processing, visual and spatial memory (3 categorical variables) at Visit 6 compared to Visit 2 based on the Cambridge Neuropsychological Test Automated Battery (CANTAB) battery of tests.

SCOPE-BD NUIG-2017-002, Statistical Analysis Plan Version 1, 19/03/2024

14. Occurrence of a hypo (manic) episodes at visits 3, 4, 5, 6 or 7, as defined by a score of >6 on the Young Mania Rating Scale (YMRS).

15. Occurrence of other adverse effects as observed on monitoring of vital signs, reported by participants or measured utilising the Patient Rated Inventory of Side Effects (PRISE) questionnaire

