Sample size	The primary outcome in this study is the Hamilton Depression Rating Scale score (HDRS). A decrease of 50% or more in the HDRS score between randomisation and Visit 6 is considered clinically meaningful, and sufficient to consider a patient to have experienced a response. We anticipate that the average HDRS score in the proposed population pre-randomisation will be 24 units and that this outcome variable will be approximately normal. Based on a review of the literature, it is estimated that a range of plausible values for the standard deviation is between 5 to 13 units. Using this information, a sample of 44 participants (22 in each group) will have 85% power to detect a difference of 12 units in mean score change between the treatment and control arms, i.e. an expected HDRS mean score of 12 in the treatment group vs. an expected HDRS mean score of 24 in the control group after Visit 6. The sample size is based on a 2-sample t-test (two-sided) with a standard deviation of 13 units (conservative approach) and a significant level of 0.05. Allocating 25 participants to each arm will ensure power $\geq 85\%$ when loss to follow-up is $< 12\%$ (6 participants missing at Visit 6 follow up).

5. Abbreviations

Ach	Acetylcholine
AE	Adverse event
AMPA	α-amino-3-hydroxy-5-methyl-4-isoxazolepropionic acid
APA	American Psychiatric Association
AR	Adverse reaction
AUDIT	Alcohol Use Disorder Identification Test
BAI	Beck Anxiety Inventory
BDI	Beck Depression Inventory
BP	Blood Pressure
BPD	Bipolar Disorder
bpm	beats per minute
CA	Competent authority
CANTAB	Cambridge Neuropsychological Test Automated Battery
CDMS	Clinical Data Management System
CGI-I	Clinical Global Impression-Improvement
CGI-S	Clinical Global Impression-Severity
CHRMs	Muscarinic cholinergic receptors
CI	Chief investigator/Co-ordinating investigator
CRA	Clinical research associate
CRF	Case report form
CRO	Contract research organisation
CT	Clinical trial
CTA	Clinical trial authorisation
DMF	Data Management File
DMP	Data Management Plan
DSM	Diagnostic Statistics Manual
DSMB	Drug Safety Monitoring Board
ECG	Electrocardiogram
ECT	Electroconvulsive Therapy
EU	European Union
GAF	Global Assessment of Functioning
GCP	Good Clinical Practice
GDPR	General Data Protection Regulation
GP	General Practitioner
HDRS	Hamilton Depression Rating Scale
HPRA	Health Products Regulatory Authority
HR	Heart Rate
HRB-CRFG	Health Research Board - Clinical Research Facility Galway
HSE	Health Service Executive

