7.3.2 Secondary Endpoints

1. Remission of depressive episode measured with the HDRS at Visit 6 compared to Visit 3.
2. Response to a depressive episode measured with the HDRS at Visit 6 compared to Visit 3.
3. Reduction of depressive symptoms (MADRS) at Visit 6 compared to Visit 3.
4. Improvement in objectively measured overall functioning (GAF) at Visit 6 compared to Visit 3.
5. Reduction in depressive symptoms as measured using the POMS after all IV infusion visits compared to before IV infusions at the same visit (Visits 2, 3, 4, 5).
6. Response and remission data measured with the HDRS at Visit 7 compared to pre-randomisation HDRS scores at Visit 3.
7. Reduction in subjectively measured mood symptoms using the POMS at follow-up visits (Visits 6 and 7) compared to pre-randomisation.
8. Reduction in depressive symptoms, measured with the MADRS at Visit 7 compared to MADRS scores at Visit 3.
9. Improvement in global functioning, measured with the GAF at Visit 7 compared to pre-infusion GAF scores at Visit 3.
10. Psychiatric inpatient admissions due to depressive episodes over the duration of the study.
11. Antidepressant medication usage or change in antidepressant medication dose due to depressive episodes over the duration of the study.
12. Adverse events over the duration of the study.
13. Post infusion side effects at all 3 IV treatment visits: Bradycardia, Hypotension, Dizziness and Sedation (Visits 3, 4 and 5)
14. Occurrence of a hypo (manic) episode over the duration of the study.
15. Improvement in motor processing, visual and spatial memory at Visit 6 compared to initial scores measured at Visit 2 or Visit 3 as measured on CANTAB.

8. Trial Design

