### 5.3 Derived variables

None of the variables related to the primary and secondary endpoints are calculated using additional variables from the data recorded in the CRF, with the exception of change scores that will be calculated as indicated in the previous 2 sections.

[figure not shown]

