## 7 Sample Size

The primary outcome in this study is the Hamilton Depression Rating Scale score (HDRS). It is judged that a decrease of 50% or more in the HDRS score between randomisation and Visit 6 will be sufficient to consider a patient to have experienced a response. We anticipate that the average HDRS score in the proposed population pre-randomisation will be 24 units and that this outcome variable will be approximately normal. Based on results from the literature, it is estimated that a range of plausible values for the standard deviation is between 5 to 13 units.

SCOPE-BD NUIG-2017-002, Statistical Analysis Plan Version 1, 19/03/2024

Using this information, a sample of 44 participants (22 in each group) will have 85% power to detect a difference of 12 units between the treatment and control arms, i.e. an expected HDRS mean score of 12 in the treatment group vs. an expected HDRS mean score of 24 in the control group after Visit 6. The sample size is based on a 2-sample t-test (two-sided) with a standard deviation of 13 units (conservative approach) and a significant level of 0.05. Allocating 25 participants to each arm will ensure power  $\geq 85\%$  when loss to follow-up is  $< 12\%$  (6 participants missing at Visit 6 follow up).

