### 8.2 Final analyses

All final analyses identified in the protocol and in this SAP will be performed after the last patient has completed the study. If a participant withdraws before completing the study, the reason for withdrawal will be documented and reported.

Before carrying out the analyses, the data manager's team at CRFG is responsible for the database cleaning process to ensure the integrity of the analyses. The database will be locked prior to the initiation of the analysis.

Any post-hoc exploratory analyses completed to support planned study analyses, which were not identified in this SAP, will be documented and reported in appendices to the Clinical Study Report (CSR).

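### The Visit 7 response endpoint is defined with the Visit 6 MADRS score, and HDRS response, listed in protocol 7.3.2, has no responder rule in the endpoint definitions of either document

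*SAP*

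**What the plan says.** **SAP 5.2.2, items 3 and 4.** Item 3 defines response after the last infusion, at Visit 6, as "a 50% reduction in MADRS score at Visit 6 compared to Visit 3". Item 4 is headed "Response to a depressive episode at follow-up (measured objectively at Visit 7" and then repeats the same criterion, including the words Visit 6. Protocol 8.12.1.2, items 3 and 4, is identical.

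**SAP 5.3.** No separate derivation is given. Endpoint variables are taken as recorded, "with the exception of change scores that will be calculated as indicated in the previous 2 sections".

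**Protocol 7.3.2.** Item 2 is "Response to a depressive episode measured with the HDRS at Visit 6 compared to Visit 3". Item 6 is "Response and remission data measured with the HDRS at Visit 7 compared to pre-randomisation HDRS scores at Visit 3". Neither states a threshold. The MADRS items in that list (3 and 8) are reductions in score, not responder endpoints.

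**Sample-size text.** The protocol synopsis says "A decrease of 50% or more in the HDRS score between randomisation and Visit 6 is considered clinically meaningful", and SAP 7 treats "a decrease of 50% or more in the HDRS score between randomisation and Visit 6" as enough to call a patient a responder. Protocol 11.2 says the same as SAP 7. None of these is an endpoint definition, and none covers Visit 7.

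**SAP 8.2.** "All final analyses identified in the protocol and in this SAP will be performed after the last patient has completed the study".

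**The concern.** There are two separate faults.

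1. The follow-up response endpoint contains no follow-up data. A programmer who follows rule (i) produces the Visit 6 table again under a Visit 7 heading. A participant seen at Visit 6 but not at Visit 7 would also be counted as having a Visit 7 outcome. A reader would take the table as evidence that response was maintained to about day 29, when it says nothing on that.

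2. The response scale is unsettled. The two endpoint lists in the protocol have no response endpoint in common: 7.3.2 uses the HDRS and 8.12.1.2 uses the MADRS. The SAP copies the second list. Two analysts could both follow the documents and differ on whether HDRS response is reported and, at Visit 7, by what rule. If that is settled after allocation is known, the choice of scale could look driven by the result.

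**Working it through.** **Step 1: compare the definitions.**

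| Endpoint | Visit in heading | Scale and visits in rule |
|---|---|---|
| SAP 5.2.2 item 3; protocol 8.12.1.2 item 3 | 6 | MADRS, Visit 6 vs Visit 3 |
| SAP 5.2.2 item 4; protocol 8.12.1.2 item 4 | 7 | MADRS, Visit 6 vs Visit 3 |
| Protocol 7.3.2 item 2 | 6 | HDRS, Visit 6 vs Visit 3, no threshold |
| Protocol 7.3.2 item 6 | 7 | HDRS, Visit 7 vs Visit 3, no threshold |

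The first two rows share scale, visits and threshold, so they agree in 100% of participants by construction. SAP 5.3 points back to the same rule. SAP 13.2 refers only to the follow-up visit specified for the endpoint, and item 4 names two visits. Remission, in the same list, has both an HDRS and a MADRS criterion at each visit, which suggests that the missing HDRS response rule was not intended.

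**Step 2: error in the reported Visit 7 rate.** Let p6 be the Visit 6 response rate, r the share of Visit 6 responders who lose response by Visit 7, and l the share of non-responders who gain it.

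- True Visit 7 rate: p7 = p6(1 − r) + (1 − p6)l
- Rate reported under item 4(i): p6
- Error: p6 − p7 = p6·r − (1 − p6)·l
- Share misclassified: p6·r + (1 − p6)·l

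Inputs: p6 from 42% to 71%, the range of IV scopolamine response rates in protocol Table 1. The documents give no figure for r or l; I assume r from 0 to 40% and l from 0 to 20%.

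| p6 | r | l | p7 | Error (points) |
|---|---|---|---|---|
| 0.42 | 0 | 0.20 | 0.42 + 0.58×0.20 = 0.536 | −11.6 |
| 0.58 | 0.20 | 0.10 | 0.58×0.80 + 0.42×0.10 = 0.506 | +7.4 |
| 0.71 | 0.40 | 0 | 0.71×0.60 = 0.426 | +28.4 |

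The first and last rows are the extremes of the grid. In the middle row the misclassified share is 0.58×0.20 + 0.42×0.10 = 0.158, or 3.5 of the 22 evaluable participants per arm.

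**Step 3: effect on the difference between arms.** Table 1 gives placebo rates of 20% and 30% in the oral scopolamine trial. With the middle-row r and l in both arms:

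- Placebo p6 = 0.20: p7 = 0.20×0.80 + 0.80×0.10 = 0.240. Reported difference 58.0 − 20.0 = 38.0 points; true 50.6 − 24.0 = 26.6; overstated by 11.4.
- Placebo p6 = 0.30: p7 = 0.30×0.80 + 0.70×0.10 = 0.310. Reported 58.0 − 30.0 = 28.0; true 50.6 − 31.0 = 19.6; overstated by 8.4.

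Equal r and l in the two arms is a further assumption.

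**Step 4: what is not affected.** The plan's sample size reproduces. A difference of 12 with SD 13, two-sided 0.05 and 22 per arm gives exact t-test power of 84.9% (stated 85%), and 44/(1 − 0.12) = 50. None of it uses a response endpoint.

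**The case against.** The strongest reply is that this is an obvious copying slip. The heading says Visit 7, the neighbouring remission item is correctly a Visit 7 endpoint, protocol 7.3.2 item 6 has response at Visit 7, and an analyst who saw two identical tables would probably notice. That reading of the intent is very likely right. But the operative rule is still wrong in both documents, nothing in the SAP corrects it, and an analyst who repairs it silently departs from the written plan.

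On the scale, HDRS and MADRS response can both be reported, SAP 8.2 keeps analyses named in the protocol in scope, and the sample-size text supplies one HDRS rule for Visit 6 with no competitor. This stands in part: the HDRS rule is hardly in doubt at Visit 6. It is unstated for Visit 7, and neither endpoint has an entry in the SAP list.

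On result-driven choice, protocol 11.1 has the analyses done blinded to allocation and SAP 8.2 requires database lock first. Both reduce the risk, but neither supplies the missing rule.

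The error range also reflects an assumed grid and scopolamine rates taken partly from subgroups of mostly unipolar, unmedicated samples. A lower placebo rate can fall outside it: p6 = 20%, r = 0, l = 20% gives −0.80×0.20 = −16.0 points. That is correct, and the figures should be read as illustration. The duplication itself needs no assumption.

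**Conclusion.** Both faults are real. Item 4(i) as written duplicates item 3(i) in every participant. The size of the resulting error in the Visit 7 rate is unknown: −11.6 to +28.4 points on the assumed scopolamine-arm grid, and +7.4 points in the middle case. Two endpoints in protocol 7.3.2, HDRS response at Visit 6 and at Visit 7, have no explicit entry in SAP 5.2.2.

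The consequence is confined to the dichotomised response endpoints. Visit 7 remission, change in HDRS and MADRS, GAF, CGI and the HDRS mixed model (SAP 13.2) are unaffected and would still show a loss of effect. SAP 10.5 treats secondary analyses as exploratory and protocol 11.7 confines significance testing to the primary analysis. The point should be corrected, but it does not threaten the trial's main conclusion.

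**What to change.** Before database lock and unblinding:

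1. In rule (i) of item 4, in SAP 5.2.2 and protocol 8.12.1.2, replace Visit 6 with Visit 7.
2. Reconcile protocol 7.3.2 with 8.12.1.2. Either add to items 3 and 4 of both lists a second criterion, a reduction of at least 50% in HDRS from Visit 3 (at Visit 6 and Visit 7 respectively), or remove HDRS response from 7.3.2 and state why.
3. Write the MADRS threshold as a reduction of at least 50%, to match the sample-size text. This is tidying; most readers would take it that way already.

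No new data, visits or participants are needed: protocol 8.3.5 and 8.3.6 schedule both scales at Visits 3, 6 and 7. The protocol edits would have to be submitted for review under protocol 15.1. The SAP correction alone repairs the analysis, so it need not wait for that.
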